2.11.3 Windows for time points

Statistical analysis will be based on the nominal visit which should follow schedule defined in protocol Section 1.2. Visits will not be windowed for analysis purposes, except for unscheduled visits in some cases as described in [Section 2.11.4](#).

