#### **10.5.3 List of criteria for permanent treatment discontinuation**

The patient may withdraw from treatment with the IMP if he/she decides to do so, at any time and irrespective of the reason, or this may be the investigator's or sponsor's decision. All efforts should be made to document the reasons for treatment discontinuation and this should be documented in the e-CRF.

Patients should discontinue the IMP for the following reasons:

- Unacceptable toxicity (see [Section 8.3.4.2](#)).
- The need for intervention or therapy precluded by protocol, and determination by the investigator that it is medically necessary to do so.
- Patient noncompliance with treatment or if the patient wishes to be withdrawn from treatment.
- The patient is no longer deriving clinical benefit, in the opinion of the investigator.
- Pregnancy

In addition, the sponsor may decide to discontinue the trial prematurely for any other reason.

Any abnormal laboratory value or ECG parameter relevant to the situation will be immediately rechecked for confirmation before making a decision of permanent discontinuation of the IMP for the concerned patient.

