#### **11.4.5 Exploratory efficacy analyses**

Efficacy assessments are described in [Section 9.2.2](#).

Efficacy analyses will be performed on the modified intent-to-treat analysis set. For each exploratory efficacy assessment, observed measures, change from baseline and/or percent change from baseline to week 52 or 64, as appropriate, will be listed and summarized using descriptive statistics overall and separately by timepoint and age cohort, including 95% confidence intervals.

Categorical variables (eg, pulmonary imaging, chest X-ray) will be summarized using frequencies and percentages according to time points collected from screening or baseline to Week 52 (or last study assessment).

The same efficacy analyses will also be performed by manufacturing scale.

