2.8.1 Spleen and liver volumes

Spleen and liver volumes will be measured by abdominal magnetic resonance imaging (MRI) to quantitate the degree of splenomegaly and hepatomegaly at Screening, Week 26 and Week 52 (or at withdrawal if withdrawn prematurely and not done within 12 weeks prior to withdrawal). MRIs will be collected and read centrally by a third party blinded to patient number and study visit.

Spleen volume ≥ 5 multiples of normal (MN) is an inclusion criterion. For screening purpose, the external vendor will provide the spleen volume in the unit of MN to the site. The computation will use the same formula as below. However, the report from the external vendor will be part of the source document of the site and will not be included in the clinical data base. Spleen and liver volumes collected in cm^3 unit (including those from the screening visit) will be converted to multiples of normal (MN) unit for analyses using the following formula:

$$\text{Spleen Volume (MN)} = \text{Spleen Volume} (\text{cm}^3) / [2 * \text{Weight (kg)}].$$

$$\text{Liver Volume (MN)} = \text{Liver Volume} (\text{cm}^3) / [25 * \text{Weight (kg)}].$$

Change from baseline and percent change from baseline for both cm^3 and MN units, in addition to observed values, will be calculated and summarized for all scheduled visits by age group cohorts and overall. The analysis of covariance (ANCOVA) with baseline as the covariate and Wilcoxon-Mann-Whitney (WMW) test p-values for the change from baseline and percent change from baseline will be provided in the summary tables for spleen/liver volumes in MN unit. Box plots of observed values over time for spleen and liver volumes in MN unit will be provided.

Summary plots for the mean spleen/liver volumes (MN) over time will be provided. By-patient plots of the observed spleen/liver volumes (MN) over time will be provided.

Additional sensitivity analyses to assess the effect of age group cohorts: Analysis of covariance (ANCOVA) will be used for the mITT population for spleen/liver volumes in MN unit with the following model:

Percent change from baseline at Week 26 or 52 volume (MN) = Age group cohorts + Baseline value

The observed values, change from baseline and percent change from baseline on spleen volume (MN) will also be summarized by the following disease severity:

- Spleen volume by baseline spleen volume severity (severe vs not severe). Severity is defined as baseline spleen volume > 15 MN.

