2.11.4 Unscheduled visits

In general, unscheduled visit measurements will not be included in the by-visit summaries, but will be used for computation of baseline and/or summaries of “any time” or “end of study” time points or PCSA. If a scheduled post-baseline visit measurement of an exploratory efficacy parameter is missing, but an unscheduled visit value for the same parameter is available in close proximity of time, the windowing of unscheduled visit to substitute the missing scheduled visit value is defined in the following table. Laboratory, vital signs, ECG and PD parameters are collected at several times during a visit with respect to the infusion time, therefore a window for an unscheduled visit to substitute missing schedule values will not be considered.

Parameter	Scheduled Visit/Target Days	Analysis Visit Window, in Study Days
Spleen volume, liver volume, pulmonary imaging with HRCT, PFT, cycle ergometry, physician's global assessment, health outcome questionnaires	Week 26/183 days Week 52/365 days	92 days to 274 days 275 days to 456 days
Chest X-ray, bone age by hand X-ray	Week 52/365 days	275 days to 456 days
Efficacy biomarker, serum bone-specific ALP and C-telopeptide	Week 26/183 days Week 52/365 days Week 64/449 days	92 days to 274 days 275 days to 407 days 408 days to 463 days
Lipid profile	Week 12/85 days Week 26/183 days Week 38/267 days Week 52/365 days Week 64/449 days	43 days to 134 days 135 days to 225 days 226 days to 316 days 317 days to 407 days 408 days to 463 days

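### The SAP lets an unscheduled visit, but not the withdrawal visit, stand in for a missing Week 26 or Week 52 efficacy value

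*SAP*

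**What the plan says.** SAP 2.11.3 sets the rule: "Statistical analysis will be based on the nominal visit which should follow schedule defined in protocol Section 1.2". It adds "Visits will not be windowed for analysis purposes, except for unscheduled visits in some cases as described in" SAP 2.11.4.

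SAP 2.11.4 supplies the exception. When a scheduled post-baseline efficacy value is missing but "an unscheduled visit value for the same parameter is available in close proximity of time", then "the windowing of unscheduled visit to substitute the missing scheduled visit value is defined in the following table". For spleen and liver volume, HRCT, PFT, ergometry, the physician's global assessment and the questionnaires, the table gives study days 92 to 274 for Week 26 and 275 to 456 for Week 52. Chest and hand X-ray have the Week 52 window only. Neither section mentions the withdrawal visit.

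Data are nevertheless collected there. For MRI, SAP 2.8.1 adds to the Week 26 and Week 52 schedule "or at withdrawal if withdrawn prematurely and not done within 12 weeks prior to withdrawal". SAP 2.8.3 (PFT), 2.8.5 to 2.8.8 (HRCT, chest X-ray, hand X-ray, ergometry) and 2.8.13 (questionnaires) have the same provision. Withdrawal has its own column in the protocol 1.2 flow chart. Protocol 10.5.4 asks for that visit, when possible, within 2 weeks of the last infusion.

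The efficacy population is every treated patient (SAP 2.2.2), and continuous variables are analysed on observed data only (SAP 2.11.2). The age-cohort ANCOVAs for spleen and liver volume (SAP 2.8.1) and for PFT (SAP 2.8.3) take percent change at Week 26 or Week 52 as the outcome.

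**The concern.** Two scans taken on the same study day are treated differently according to the visit label. An unscheduled MRI on day 300 can serve as the Week 52 value; a withdrawal MRI on day 300 cannot. The SAP gives no reason.

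The withdrawal value is usually the last one available. SAP 2.6.1.6 says that a patient who permanently stops treatment is withdrawn from the study, so no later Week 52 value should be expected. If the visit takes place as protocol 10.5.4 asks, the value is close to the last infusion and still informative about treatment.

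The stopping reasons in protocol 10.5.3 include unacceptable toxicity and "The patient is no longer deriving clinical benefit, in the opinion of the investigator". Missing Week 52 values could therefore be related to response. Patients who stop early would belong to the efficacy population but be absent from its Week 52 means, confidence intervals and p-values, although a measurement had been taken. HRCT, chest X-ray and hand X-ray are most exposed, because Week 52 is their only scheduled post-baseline visit.

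**Working it through.** **1. Reproduce the plan's windows.** Target day = 7 x week + 1, so Week 26 is day 183 and Week 52 is day 365. The limits are midpoints between successive targets, starting from day 1:
- Week 26 lower limit: (1 + 183)/2 = 92.
- Week 26 upper limit: (183 + 365)/2 = 274.
- Week 52: 275 to 365 + 91 = 456.

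This matches the table row "92 days to 274 days 275 days to 456 days".

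**2. Find when a withdrawal MRI or PFT is due.** It is due when the last one is more than 84 days old. Inputs: screening on day -60 or day -1; the Week 26 and Week 52 tests done 0 or 7 days after the infusion; withdrawal on any day from 1 to 462.
- Due before Week 26: from day 26 (early screening) or day 85 (late screening) to day 182 or 189.
- Due again: days 268 to 364, or 275 to 371.
- Due again: from day 450 or 457 to day 462.

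That is 208 to 267 due days, of which 195 lie inside a window: 195/267 = 73% and 195/208 = 94%. When tests are done on the infusion day, 14 of the 195 (days 268 to 274 and 450 to 456) fall where a Week 26 or Week 52 value normally already exists. The count that could fill a gap is then 195 - 14 = 181, or 68% to 87%. These are shares of calendar days, not of expected withdrawals.

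**3. Repeat for HRCT.** A withdrawal HRCT is due on 293 to 352 days, and 280 of these lie in a listed window. Only 97 are in the Week 52 window. The other 183 (days 92 to 274) are in the Week 26 window, although no Week 26 HRCT is scheduled in protocol 1.2 or SAP 2.8.5. The table needs correcting on this point in any case.

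**4. Check who stays outside.** MRI or PFT values from withdrawals before day 92 fit no window. Without repeated doses, the two 0.3 mg/kg infusions fall on days 29 and 43, so patients replaced for not tolerating them would normally leave before day 92. They remain in the efficacy population.

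**5. Illustrate the size.** The documents give no dropout rate and no expected pediatric effect. Assume 20 patients, of whom k = 1 to 4 stop early with a usable withdrawal value. Assume completers average -25.3% in spleen volume (the adult 26-week figure, protocol 4.1) and stoppers average m.

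Mean = [(20 - k) x (-25.3) + k x m]/20

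| m | k = 1 | k = 2 | k = 3 | k = 4 |
|---|---|---|---|---|
| 0 | -24.0 | -22.8 | -21.5 | -20.2 |
| -12.65 | -24.7 | -24.0 | -23.4 | -22.8 |
| -25.3 | -25.3 | -25.3 | -25.3 | -25.3 |

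Under the current rule the reported mean is -25.3% in every cell.

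**6. Look at the cohorts.** The protocol minimums are 3 adolescents, 3 + 4 = 7 children and 2 + 2 = 4 infants/early children. One patient is 33%, 14% and 25% of these. In a cohort of 4 with one stopper, the mean would be 3 x (-25.3)/4 = -19.0% at no effect and (3 x (-25.3) - 12.65)/4 = -22.1% at half effect. The minimums sum to 14, below the planned 20, so at least one cohort will exceed its minimum.

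**The case against.** A reader might infer that withdrawal data are discarded. The documents do not say so. SAP 2.8 has observed values and changes listed and summarised, SAP 2.8.1 and 2.8.3 plan by-patient plots for MRI and PFT, and Withdrawal is a column of the schedule that defines nominal visits, so a separate Withdrawal row is compatible with the text. This part of the objection stands. What is missing is a route into the Week 26 and Week 52 results, and a Withdrawal row does not provide one.

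A reader might also infer that the SAP silently dropped a carry-forward rule. Protocol 11.4.5 tabulates categorical imaging over "time points collected from screening or baseline to Week 52 (or last study assessment"). That may describe only the span of time points shown: the synopsis sentence on the same variables refers to Week 52 or Week 64 as appropriate. The phrase is ambiguous, so it supports a request to reconcile the texts, not a charge of undeclared departure.

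Keeping a strictly nominal Week 52 estimate is defensible, since windowing mixes in shorter treatment. But the SAP already accepts an unscheduled value from day 275, which is 365 - 275 = 90 days early. The argument therefore does not justify treating the two kinds of visit differently.

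The direction of bias is not established. Protocol 10.5.3 also lists patient choice, noncompliance, precluded therapy and pregnancy, and a patient who stops for toxicity need not be a poor organ responder. Efficacy is exploratory in a single-arm safety study without a power calculation, and SAP 2.11.2 leaves room for other missing-data strategies. The only one named, for DLco in SAP 2.8.3, is optional and has no method.

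**Conclusion.** The concern holds as a gap in the visit rules. Read as written, withdrawal values cannot enter the Week 26/52 change-from-baseline summaries or the ANCOVAs fixed at those weeks, while an unscheduled value from the same day can. It does not hold as a claim that data are lost or that results are shown to be inflated.

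The size is unknown. In the illustration the overall mean moves by 1.3 points (one stopper, no effect) to 5.1 points (four stoppers, no effect), by 0.6 to 2.5 points at half effect, and not at all at equal effect. This rests on a borrowed adult figure, an assumed number of stoppers and usable withdrawal values for all of them. A single cohort could move more, because one patient is 25% of the minimum infant/early child cohort. The safety conclusions are unaffected. The point is worth correcting because exploratory efficacy is part of a secondary objective and is to be reported with p-values and confidence intervals.

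**What to change.** In SAP 2.11.3 and 2.11.4:
- Apply the existing window table to withdrawal-visit values when the nominal value is missing.
- Flag each such value with study day and days since last infusion.
- Report the number of patients contributing at each visit.
- Show the nominal-visit-only result as a sensitivity analysis.
- Remove HRCT from the Week 26 row.
- For HRCT, chest X-ray and hand X-ray taken at withdrawal before day 275, add a separate summary of the last on-study assessment. Do not relabel these images as Week 52.

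In SAP 1.5, state how this relates to the wording of protocol 11.4.5.

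The cost is a few sentences, a derivation flag and one or two extra tables, with no new data. The downside is that some values would reflect shorter treatment, by up to 90 days at Week 52 and 183 - 92 = 91 days at Week 26, as the SAP already allows for unscheduled visits. MRI and PFT values from withdrawals before day 92 would still fit no window; the counts per visit would make that visible.

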2.11.4 Unscheduled visits

In general, unscheduled visit measurements will not be included in the by-visit summaries, but will be used for computation of baseline and/or summaries of “any time” or “end of study” time points or PCSA. If a scheduled post-baseline visit measurement of an exploratory efficacy parameter is missing, but an unscheduled visit value for the same parameter is available in close proximity of time, the windowing of unscheduled visit to substitute the missing scheduled visit value is defined in the following table. Laboratory, vital signs, ECG and PD parameters are collected at several times during a visit with respect to the infusion time, therefore a window for an unscheduled visit to substitute missing schedule values will not be considered.

Parameter	Scheduled Visit/Target Days	Analysis Visit Window, in Study Days
Spleen volume, liver volume, pulmonary imaging with HRCT, PFT, cycle ergometry, physician's global assessment, health outcome questionnaires	Week 26/183 days Week 52/365 days	92 days to 274 days 275 days to 456 days
Chest X-ray, bone age by hand X-ray	Week 52/365 days	275 days to 456 days
Efficacy biomarker, serum bone-specific ALP and C-telopeptide	Week 26/183 days Week 52/365 days Week 64/449 days	92 days to 274 days 275 days to 407 days 408 days to 463 days
Lipid profile	Week 12/85 days Week 26/183 days Week 38/267 days Week 52/365 days Week 64/449 days	43 days to 134 days 135 days to 225 days 226 days to 316 days 317 days to 407 days 408 days to 463 days

2.11.5 Potentially clinically significant abnormalities (PCSA) criteria

In the safety data analysis, patients included in the PCSA analysis for a given parameter will be defined as subjects:

- Exposed to study treatment,
- With at least one parameter result after study treatment administration, and,
- With available laboratory limits when required for analysis.

Liver function tests

ALT	> 3 ULN By distribution analysis: > 3 ULN > 5 ULN > 10 ULN > 20 ULN
AST	> 3 ULN By distribution analysis: > 3 ULN > 5 ULN > 10 ULN > 20 ULN
Alkaline phosphatase	> 1.5 ULN
Total bilirubin	>= 1.3 ULN
ALT and total bilirubin	ALT > 3 ULN and total bilirubin > 2 ULN

Hematology

WBC	Birth/0 to 27 days old (Neonates)	<4.0 GIGA/L >25.0 GIGA/L
	28 days/1 month to 23 months old (Infants)	<4.0 GIGA/L >20.0 GIGA/L
	24 months/2 years to <6 years old (Children)	<3.0 GIGA/L >16.0 GIGA/L
	6 to <12 years old (Children)	<5.0 GIGA/L >17.0 GIGA/L
	12 to 16/18 years old (Adolescents)	<4.5 GIGA/L >13.5 GIGA/L
Lymphocytes	Birth/0 to 27 days old (Neonates)	<1.2 GIGA/L >17.0 GIGA/L
	28 days/1 month to 23 months old (Infants)	<2.0 GIGA/L >13.5 GIGA/L
	24 months/2 years to <6 years old (Children)	<1.0 GIGA/L >9.5 GIGA/L
	6 to <12 years old (Children)	<1.0 GIGA/L >8.0 GIGA/L
	12 to 16/18 years old (Adolescents)	<0.6 GIGA/L >6.0 GIGA/L

Neutrophils	Birth/0 to 27 days old (Neonates)	<4.0 GIGA/L (1 day old) <1.5 GIGA/L (2 – 7 days old) <1.25 GIGA/L (>7 day – 1 month old) >1 ULN
	28 days/1 month to 23 months old (Infants)	<1.0 GIGA/L (1 – 3 months) <1.2 GIGA/L (3 – 24 months) >1 ULN
	24 months/2 years to <6 years old (Children)	<1.2 GIGA/L >1 ULN
	6 to <12 years old (Children)	<1.2 GIGA/L >1 ULN
	12 to 16/18 years old (Adolescents)	<1.2 GIGA/L >1 ULN
Eosinophils	All age ranges	>0.5 GIGA/L Or >ULN if ULN \geq 0.5 GIGA/L
Hemoglobin	Birth/0 to 27 days old (Neonates)	<12.0 g/dL and 20% decrease from baseline, or decrease from baseline \geq 2 g/dL
	28 days/1 month to 23 months old (Infants)	<9.0 g/dL and 20% decrease from baseline, or decrease from baseline \geq 2 g/dL
	24 months/2 years to <16/18 years old (Children, Adolescents)	<10.0 g/dL and 20% decrease from baseline, or decrease from baseline \geq 2 g/dL
Hematocrit	Birth/0 to 27 days old (Neonates)	<0.39 l/l or 40% >0.61 l/l or 47%
	28 days/1 month to 23 months old (Infants)	<0.29 l/l or 29% >0.42 l/l or 42%
	24 months/2 years to <16/18 years old (Children, Adolescents)	<0.32 l/l or 32% >0.47 l/l or 47%
Platelets	All age ranges	<100 GIGA/L and 20% decrease from baseline \geq 700 GIGA/L

ECG parameters

HR	Birth/0 to 27 days old (Neonates)	<=90 bpm and decrease from baseline >=20 bpm >=190 bpm and increase from baseline >=20 bpm
	28 days/1 month to 23 months old (Infants)	<=80 bpm and decrease from baseline >=20 bpm >=175 bpm and increase from baseline >=20 bpm
	24 months/2 years to <6 years old (Children)	<=75 bpm and decrease from baseline >=20 bpm >=140 bpm and increase from baseline >=20 bpm
	6 to <12 years old (Children)	<=50 bpm and decrease from baseline >=20 bpm >=120 bpm and increase from baseline >=20 bpm
	12 to 16/18 years old (Adolescents)	<=50 bpm and decrease from baseline >=20 bpm >=120 bpm and increase from baseline >=20 bpm
PR	Birth/0 to 27 days old (Neonates)	>=120 ms
	28 days/1 month to 23 months old (Infants)	>=140 ms
	24 months/2 years to <6 years old (Children)	>=160 ms
	6 to <12 years old (Children)	>=170 ms
	12 to 16/18 years old (Adolescents)	>=180 ms
QRS	Birth/0 to 27 days old (Neonates)	>=85 ms
	28 days/1 month to 23 months old (Infants)	>=85 ms
	24 months/2 years to <6 years old (Children)	>=95 ms
	6 to <12 years old (Children)	>=100 ms
	12 to 16/18 years old (Adolescents)	>=110 ms
QTc	Birth/0 to <12 years old (Neonates, Infants, Children)	Absolute values (ms) Borderline: 431 – 450 ms Prolonged: >450 ms Additional: >=500 ms
		Increase from baseline Borderline: Increase from baseline 30 – 60 ms Prolonged: Increase from baseline >60 ms

12 to 16/18 years old (Adolescents)	Absolute values (ms) Borderline: 431 – 450 ms (Boys); 451 – 470 ms (Girls) Prolonged: >450 ms (Boys); >470 ms (Girls) Additional: >=500 ms
	Increase from baseline Borderline: Increase from baseline 30 – 60 ms Prolonged: Increase from baseline >60 ms

Clinical chemistry

Creatinine	Birth/0 to <6 years old (Neonates, Infants, Children)	>53 µmol/L or 0.6 mg/dL
	6 years to <12 years old (Children)	>=90 µmol/L or 1.1 mg/dL
	12 years to 16/18 years old (Adolescents)	>=132 µmol/L or 1.5 mg/dL
Blood urea nitrogen (BUN)	Birth/0 to 27 days old (Neonates)	>=4.3 mmol/L or 12 mg/dl
	28 days/1 month to 16/18 years old (Infants, Children, Adolescents)	>=6.4 mmol/L or 18 mg/dl
Chloride	All age ranges	<80 mmol/L >115 mmol/L
Sodium	All age ranges	<=129 mmol/L >=150 mmol/L
Potassium	Birth/0 to 27 days old (Neonates)	<=3.0 mmol/L >=7.0 mmol/L
	28 days/1 month to 23 months old (Infants)	<=3.5 mmol/L >=6.0 mmol/L
	24 months/2 years to 16/18 years old (Children, Adolescents)	<=3.5 mmol/L >=5.5 mmol/L
Glucose	All age ranges	Hypoglycaemia <2.7 mmol/L Hyperglycaemia >=7 mmol/L (fasted after >12 hours of fast); >=10.0 mmol/L (unfasted)

Vital signs

Heart rate	Birth/0 to 27 days old (Neonates)	<=90 bpm and decrease from baseline >=20 bpm >=190 bpm and increase from baseline >=20 bpm
	28 days/1 month to 23 months old (Infants)	<= 80 bpm and decrease from baseline >=20 bpm >= 175 bpm and increase from baseline >= 20 bpm
	24 months/2 years to <6 years old (Children)	<= 75 bpm and decrease from baseline >=20 bpm >= 140 bpm and increase from baseline >= 20 bpm
	6 to <12 years old (Children)	<=50 bpm and decrease from baseline >=20 bpm >=120 bpm and increase from baseline >=20 bpm
	12 to 16/18 years old (Adolescents)	<=50 bpm and decrease from baseline >=20 bpm >=120 bpm and increase from baseline >=20 bpm
Systolic BP	Birth/0 to 27 days old (Neonates)	<=60 mmHg and decrease from baseline >=20 mmHg >=85 mmHg and increase from baseline >=20 mmHg
	28 days/1 month to 23 months old (Infants)	<=70 mmHg and decrease from baseline >=20 mmHg >=98 mmHg and increase from baseline >=20 mmHg
	24 months/2 years to <6 years old (Children)	<=70 mmHg and decrease from baseline >=20 mmHg >=101 mmHg and increase from baseline >=20 mmHg
	6 to <12 years old (Children)	<=80 mmHg and decrease from baseline >=20 mmHg >=108 mmHg and increase from baseline >=20 mmHg
	12 to 16/18 years old (Adolescents)	<=90 mmHg and decrease from baseline >=20 mmHg >=119 mmHg and increase from baseline >=20 mmHg
Diastolic BP	Birth/0 to 27 days old (Neonates)	<=34 mmHg and decrease from baseline >=10 mmHg >=50 mmHg and increase from baseline >=10 mmHg
	28 days/1 month to 23 months old (Infants)	<=34 mmHg and decrease from baseline >=10 mmHg >=54 mmHg and increase from baseline >=10 mmHg
	24 months/2 years to <6 years old (Children)	<=34 mmHg and decrease from baseline >=10 mmHg >=59 mmHg and increase from baseline >=10 mmHg
	6 to <12 years old (Children)	<=48 mmHg and decrease from baseline >=10 mmHg >=72 mmHg and increase from baseline >=10 mmHg
	12 to 16/18 years old (Adolescents)	<=54 mmHg and decrease from baseline >=10 mmHg >=78 mmHg and increase from baseline >=10 mmHg

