2.6 ANALYSIS OF SAFETY DATA

Safety endpoints include data pertaining to the safety and tolerability of olipudase alfa: assessment of adverse events (AEs)/treatment-emergent adverse events (TEAEs), including AESIs (eg, infusion-associated reactions (IARs), symptomatic overdose, etc.); physical examinations; neurological examinations; clinical laboratory evaluations; vital sign measurements; ECGs; Doppler echocardiography; liver ultrasound Doppler; safety biomarkers; and immune response assessments. For laboratory endpoints, the summaries will use both the international system of units (SI) and US conventional units; figures will use the international system of units (SI); data listings will provide the results in original units as well as in standard units, where applicable.

All the safety analyses will be performed using the safety population. Patients will be summarized and displayed by age group cohorts and overall. Safety data will be reported up to and including the time of treatment withdrawal, and follow-up for AEs, where applicable. The baseline value is the last available value before the first infusion of olipudase alfa, except for white blood cell count, platelet count, hemoglobin and possibly ECG parameters. For complete definition of baseline, refer to [Section 2.11.1](#).

For all safety data, the observation period will be divided into 2 segments:

- The **pretreatment period** is defined as the time between when the patient gives informed consent and the start of the first infusion (excluded).
- The **on-treatment period** is defined as the time from the start of the first infusion (included) till the end of the study.

The following definitions regarding potentially clinically significant abnormality (PCSA) will be applied to laboratory parameters, vital signs and ECG:

The PCSA values are defined as abnormal values considered medically important by the sponsor according to predefined criteria/thresholds based on literature review and defined by the sponsor for clinical laboratory tests, vital signs, and ECG. These values are provided in [Section 2.11.5](#).

- PCSA criteria will determine which patients had at least 1 PCSA taking into account all evaluations performed, including unscheduled or repeated evaluations.
- Before determining a value as PCSA, the value will be rounded to the precision that the PCSA criterion is defined.

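### Two PCSA cut-offs in SAP 2.11.5 (neonatal hematocrit; creatinine at 6 to <12 years) are printed in two units that do not match, and no unit is named as governing the flag

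*SAP*

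**What the plan says.** SAP 2.11.5 lists the PCSA thresholds, several of them in two units. The rows that matter here are:

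- Creatinine, birth to <6 years: ">53 µmol/L or 0.6 mg/dL"
- Creatinine, 6 to <12 years: ">=90 µmol/L or 1.1 mg/dL"
- Creatinine, 12 to 16/18 years: ">=132 µmol/L or 1.5 mg/dL"
- Hematocrit, 0 to 27 days: "<0.39 l/l or 40% >0.61 l/l or 47"
- Hematocrit, 28 days to 23 months: "<0.29 l/l or 29% >0.42 l/l or 42"
- Hematocrit, 2 to <16/18 years: "<0.32 l/l or 32% >0.47 l/l or 47"

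(The last figure in each hematocrit quote is a percentage.)

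Two rules in SAP 2.6 bear on how these are used. On units, for laboratory endpoints "the summaries will use both the international system of units (SI) and US conventional units". On classification, "Before determining a value as PCSA, the value will be rounded to the precision that the PCSA criterion is defined". SAP 2.6.5 then plans PCSA summaries for hematology and clinical chemistry by age cohort and overall, with separate listings.

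Protocol 9.1.8 says laboratory values are converted to international units for analysis and that tables and listings use those units. Neither document says which unit decides whether a value is a PCSA.

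**The concern.** A dual-unit threshold should be one quantity written twice. In two rows it is not, so a sample that falls between the two printed values is abnormal or normal depending on the column the programmer reads. Safety is the primary endpoint, and these counts are part of its planned output. Neither criterion has a change-from-baseline condition, so the cut-off alone determines the flag. With laboratory summaries planned in both unit systems, an SI table and a US-unit table could give different PCSA counts from the same data. A second programmer could also fail to reproduce the first one's count without either having made a mistake.

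**Working it through.** **Hematocrit (needs no outside figure).** Percent = 100 × l/l.

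| Row | Low: l/l as % vs printed % | High: l/l as % vs printed % |
|---|---|---|
| 0 to 27 days | 39 vs 40 | 61 vs 47 |
| 28 days to 23 months | 29 vs 29 | 42 vs 42 |
| 2 to <16/18 years | 32 vs 32 | 47 vs 47 |

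Only the neonatal row fails. Its upper limit is 61 − 47 = 14 points apart: a value above 47% and up to 61% is a PCSA in percent and not in l/l (0.50 l/l = 50% is an example). On the low side, values from 39% to below 40% split in the same direction. Rounding to the printed precision moves the edges by half a point (47.5 to 61.5 and 38.5 to 39.5) and leaves the widths unchanged. The neonatal 47% equals the upper limit of the oldest row, which may be a copying slip.

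**Creatinine.** The documents print no conversion factor. I assume 10,000/113.12 = 88.4 µmol/L per mg/dL.

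| Row | Implied ratio | SI value in mg/dL | mg/dL value in µmol/L | Gap |
|---|---|---|---|---|
| 53 / 0.6 | 88.3 | 0.600 | 53.0 | 0.1% |
| 90 / 1.1 | 81.8 | 1.018 | 97.2 | 8.0% |
| 132 / 1.5 | 88.0 | 1.493 | 132.6 | 0.5% |

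The BUN rows agree with each other: 12/4.3 = 2.79 and 18/6.4 = 2.81 mg/dL per mmol/L.

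*Could rounding of the printed figures explain 90 / 1.1?* The pair would need a factor between 89.5/1.15 = 77.8 and 90.5/1.05 = 86.2, which excludes 88.4. Treated the same way, the 132 / 1.5 row allows 131.5/1.55 = 84.8 to 132.5/1.45 = 91.4. From the documents alone, then, a factor of 84.8 to 86.2 would fit both rows. The creatinine finding therefore rests on the assumed factor; the hematocrit finding does not. Over an assumed 85 to 90, 90 µmol/L is 1.06 to 1.00 mg/dL and 1.1 mg/dL is 93.5 to 99.0 µmol/L.

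**Creatinine after the SAP rounding rule** (whole µmol/L, one decimal in mg/dL, halves rounded up):

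- 90 / 1.1: flagged in SI from 89.5; in mg/dL from 1.05 × 88.4 = 92.8 µmol/L. Values from 89.5 to 92.8 are flagged in SI only (width 3.3).
- 53 / 0.6 (strictly greater): SI from 53.5; mg/dL from 0.65 × 88.4 = 57.5. Values from 53.5 to 57.5 are flagged in SI only (width 4.0).
- 132 / 1.5: SI from 131.5; mg/dL from 1.45 × 88.4 = 128.2. Values from 128.2 to 131.5 are flagged in mg/dL only (width 3.3).

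So once rounding is applied, the correctly converted rows have bands of similar width. The cause there is one-decimal precision in mg/dL, not a misprint.

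**Reach.** Protocol 11.1 guarantees at least 3 + 4 = 7 child-cohort patients out of at least 20. At 7 patients, one reclassification moves the cohort percentage by 1/7 = 14.3 points.

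**The case against.** The strongest reply is that the protocol already settles the unit. Section 9.1.8 prescribes international units, SI is printed first in the dual-unit rows, and SAP 2.6 adds US units to summaries without saying that PCSAs are derived a second time. If flags are set in SI only, no count changes. This stands in part: conflicting tables are possible, not planned. It does not close the gap, because SAP 2.6 departs from 9.1.8 on tables and names no unit for PCSAs. SAP 1.5 is silent on the change, but it covers only the protocol's statistical section, so its silence says little either way.

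Several stronger readings are tempting, and the documents do not support them:

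- *That creatinine values of 90 to 97 µmol/L are discordant.* That ignores the rounding rule, which ends the band at about 92.8.
- *That seven patients are affected.* Seven is the minimum number to whom the row applies. A patient changes status only with a value in the band and no other value flagged in both units. The documents give no creatinine distribution, so the number may be zero.
- *That only this creatinine row depends on the unit.* After rounding, its neighbours do too.
- *That the hematocrit error will distort results.* The row covers ages 0 to 27 days. Under the Protocol 1.4 schedule, post-dose hematology falls at 48 hours after Day 1 and next at Week 12. At most one scheduled post-dose sample per neonate would therefore be taken at an age in this row. Protocol 4.1 says type B disease is typically diagnosed after age 2, although eligibility runs from birth.
- *That patient management is at stake.* The specific laboratory triggers in Protocol 8.3.4.2.1 use neither creatinine nor hematocrit.

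Reading the word between the two units as meaning that either one triggers the flag does not help. It would leave 0.39 l/l, 0.61 l/l and 1.1 mg/dL with no function.

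**Conclusion.** The point holds in a limited form. Two dual-unit PCSA cut-offs are internally inconsistent, and the plan does not say which unit governs. The neonatal hematocrit mismatch is certain and large (14 points at the upper limit, 1 at the lower), but it matters only if a patient aged 0 to 27 days enrols. The creatinine mismatch at 6 to <12 years is 8.0% as printed and, after rounding, a band of about 89.5 to 92.8 µmol/L. It rests on the assumed factor of 88.4. Values outside these bands are classified the same way in both units. The consequence is a descriptive safety count that may not be reproducible, not a wrong decision on any patient. It is still worth correcting, because these thresholds are operative and the correction is cheap.

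**What to change.** Two changes to the SAP:

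1. In 2.11.5, the sponsor reconciles the neonatal hematocrit pair and the creatinine pair for 6 to <12 years against the source thresholds it intended. This review does not choose the values.
2. In 2.6 or 2.11.5, add one rule: each PCSA flag is derived once, in a single governing unit (SI, consistent with Protocol 9.1.8), and carried unchanged into any US-unit table or listing.

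The second change matters more, because it also removes the rounding bands in the rows that convert correctly. Flags should not be re-derived from rounded US-unit cut-offs. For example, rewriting 90 µmol/L as 1.0 mg/dL would flag from 0.95 × 88.4 = 84.0 µmol/L, giving a discordant band of 84.0 to 89.5, which is 5.5 wide against 3.3 now.

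The cost is two table rows and one programming rule, with no new data and no change to any assessment.
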